### **8.2 Withdrawal from Study**

Subjects are free to withdraw from participation in the study at any time upon request. Reasons for withdrawal from the study includes:

- Withdrawal of consent from study participant.
- Subjects who initiate maintenance dialysis.
- Subjects who receive a kidney transplant.

Subjects who initiate maintenance dialysis or who receive a kidney transplant, but have not withdrawn consent from study participation, will have a vital status check performed at 30-days following the relevant event. Vital status (alive vs. deceased) will be ascertained using available methods (e.g., phone call, in-person interaction, medical record, dialysis facility records, public records).

Subjects who withdraw their consent will discontinue study drug and be considered an early termination. The reason for subject discontinuation or withdrawal from the study will be recorded in source documentation and in the eCRF. The early termination date will be considered the End of Study date.

### **8.3 Lost to Follow-Up**

A subject will be considered lost to follow-up if he or she fails to return for 2 consecutive scheduled in-person or phone visits and is unable to be contacted by the study site staff.

The following actions must be taken if a subject fails to be available for a required study visit:

- The site will attempt to contact the subject and counsel the subject on the importance of maintaining the assigned visit schedule and ascertain if the subject wishes to and/or should continue in the study.
- Before a subject is deemed lost to follow-up, the Investigator or designee will make every effort to regain contact with the subject (a minimum of 3 documented telephone calls, or e-mails or certified letter to subject's listed address). These contact attempts should be documented in the subject's medical record or source documentation.
- Should the subject continue to be unreachable, he or she will be considered to have withdrawn from the study with a primary reason of lost to follow-up.
- Available methods (e.g., phone call, in-person interaction, medical records, dialysis facility records, public records) will be used to attempt to ascertain dialysis status, transplant status, and vital status for all subjects deemed lost to follow-up. This ensures that the data set(s) produced as an outcome of the study is/are as comprehensive as possible.

## **9.0 STUDY ASSESSMENTS AND PROCEDURES**

### **9.1 General Study Periods**

#### **9.1.1 Screening, Enrollment, and/or Randomization**

Written informed consent must be obtained prior to the subject entering the study and before protocol-directed procedures are performed. Study visits are intended to coincide with the standard of care (SOC) nephrology visit. Initial informed consent discussion, in most cases, will occur at a SOC visit.

- The *Screening period* will be a maximum of 45 days in duration. It is defined as the period of 45 days prior to Day 1 (Baseline). Local laboratory assessments used for eligibility must be within 45 days prior to Day 1, with the exception of eGFR which must be within 90 days of Day 1

If found eligible (and informed consent has been obtained), the subject will be randomized. Dosing will begin on Day 1.

The Screening laboratory values will be defined as the most recent local laboratory assessments obtained prior to Day 1 (within 45 days) with the exception of eGFR which must be within 90 days of Day 1.

### **9.1.2 Treatment Period**

The treatment period of this study includes the following visits:

- Baseline/Day 1 Visit
- Treatment Period: 270 days (9 months)

Each randomized subject will complete 5 study visits during the Treatment Period (2 in-person and 3 telephone/virtual or in-person). Study visits during the treatment period are intended to be conducted as part of routine scheduled clinical encounters.

Every attempt should be made to complete all study visits within the window as outlined in the SoA. If a visit is missed, the reason for the missed visit should be documented in the source chart.

The monitoring of iron indices and serum phosphate is required at least every 3 months and failure to monitor these parameters will be considered a protocol deviation.

### **9.1.3 End of Treatment Visit**

Subjects completing study treatment will undergo a final in-person visit at Month 9 according to the SoA (Section 1.3).

### **9.1.4 Month 10/End of Study (EOS)**

There is a 30-day safety follow-up visit after the Month 9 visit which will be performed via a telephone call/virtual visit.

Any subject who either receives a kidney transplant or initiates maintenance dialysis, and has not withdrawn consent from study participation, will have a vital status check (alive or deceased) performed at 30-days following the relevant event.

## **9.2 Clinical Assessments**

The following clinical assessments will be conducted during the study, according to the SoA (Section 1.3).

### **9.2.1 Medical History and Demographics**

- Medical History and Demographics: Targeted medical history and demographic information will be collected. Targeted medical history will include an assessment of relevant medical history with particular emphasis on medical conditions that may lead to exclusion. Significant ongoing medical conditions or diseases should be documented.

Only the starting year of a condition will be required (e.g., not month or day). For conditions that may have multiple occurrences (e.g., myocardial infarction), only the year of the most recent event will be captured.

- Targeted relevant surgical history will be captured.
- The primary cause of CKD, current transplant status and current dialysis access (if applicable), will be collected.

### **9.2.2 Vital Sign Measurement**

Heart rate, blood pressure, and weight may be collected from data available in the clinical encounter for in-person visits.

Height may be collected either from data available in the clinical record or from subject self-reported height. Height will be collected at Baseline/Day 1 only.

### **9.3 Efficacy Assessments**

The primary endpoint is the time to a composite endpoint of initiation of maintenance dialysis or all-cause mortality. It will be considered as confirmatory evidence of efficacy.

### **9.4 Laboratory and Other Assessments**

Laboratory assays will be conducted by each sites' local laboratory. Given the requirement for all subjects to have advanced NDD-CKD it is anticipated that Investigators will collect the laboratory assessments described in the SoA at intervals no less frequent than quarterly. All Investigators will receive protocol specific training regarding the anticipated laboratory assessment schedule. Routine laboratory values, as required in the SoA, will be documented in the source documentation and eCRF.

Results of these laboratory assays will be reviewed by the primary treating nephrologist, Investigator, or designee as a part of routine SOC.

Investigators or their designee are required to acknowledge and review the local laboratory test results, however, they will not be required to provide independent assessment of SOC laboratory test results with regard to their 'clinical significance' or to direct intervention (**except as noted below**). Review of the laboratory parameters should be captured in the subject source documentation.

#### **Phosphorus and Iron Indices**

**Collection and evaluation of phosphorus and iron indices (TSAT and ferritin) must be performed and reviewed at an interval no less than quarterly. Failure to monitor these parameters is considered an important protocol deviation.**

In all instances in which phosphorus and iron indices are collected, the Investigator must independently review these results to assess clinical significance and determine whether study drug dose changes or temporary discontinuation are required. Timely review of the laboratory assessments by the Investigator or designee is anticipated. Appropriate documentation of clinical

significance and any resulting dose adjustments will be documented in the subject source documentation and eCRF.

In the event the Investigator determines that a specific quarterly assessment of phosphorus and iron indices (TSAT and ferritin) is outside SOC, a study-specific lab kit will be provided by the sponsor and used to collect blood for assessment of TSAT, ferritin, and phosphorus by a central laboratory. Central laboratory details are provided in a laboratory information sheet.

Blood or urine will be collected for the following laboratory evaluations listed below and will be conducted during the course of the study. For details regarding the timing of these assessments refer to Section 1.3.

- Pregnancy Test: A serum or urine pregnancy test will be performed according to the SoA (Section 1.3) for females of childbearing potential. These results must be available and must be negative before the subject takes the first dose of study drug. Additional serum or urine pregnancy tests may be conducted throughout the study at the discretion of the Investigator to establish the absence of pregnancy during the study.

**Table 2 Typical Quarterly Laboratory Assessments**

| Hematology                  | Iron Indices  | Serum Chemistry  |
|-----------------------------|---|--|
| Complete Blood Count        | Ferritin*
TSAT*
Total iron
Total iron binding capacity | Phosphorus*
Calcium
Renal Panel (sodium, potassium, bicarbonate, chloride, BUN, creatinine, glucose)
Hepatic Panel (albumin, AST, ALT total bilirubin, ALP, total protein)
Magnesium
eGFR |
| Additional Laboratory Tests | Urine Tests   |  |
| PTH
Cystatin-C           | Urine albumin or protein; creatinine ratio                      |  |

ALP: alkaline phosphatase; AST: aspartate aminotransferase; ALT: alanine aminotransferase; BUN: blood urea nitrogen; eGFR: estimated glomerular filtration rate; PTH: parathyroid hormone; TSAT: transferrin saturation.

\*Assessment required at a frequency of no less than quarterly (90 days).

## 9.5 Safety and Other Assessments

### 9.5.1 Concomitant Medication Recording

Routine concomitant medications (name, indication for use, route, start and stop dates), including prescription and over the counter medications will be collected at Screening, Day 1, and Month 9.

Concomitant medications of interest will be captured beginning at Screening and then at each subsequent study visit.

The concomitant medications of interest include:

- Erythropoietin Stimulating Agents (ESA)
- All forms of oral or IV iron excluding oral iron in multivitamins
- All phosphate-lowering therapy
- HIF-Stabilizers

For medications of interest, the name, indication, dose, route of administration, frequency and start/stop date will be collected and captured in the source documentation and in the eCRF.

Blood Transfusions will be captured and recorded in the source and eCRF.

### **9.5.2 Adverse Event Assessment**

Auryxia (ferric citrate) is approved by the FDA for use as an oral iron replacement product in adult patients with NDD-CKD and iron deficiency at doses up to 12 tablets per day which is 100% (2 times) greater than the maximum dose allowed in this clinical study.

The safety profile of ferric citrate in the NDD-CKD population has been described by the FDA in the Auryxia USPI and by Akebia Therapeutics, Inc. in the Investigators Brochure.

**As such, adverse events will only be collected in the following instances:**

If they meet the definition of an SAE (see Section 9.6.1.2) or meet the requirements for reporting as an IND safety report. If there is any doubt whether the information constitutes an AE or SAE, please contact the Medical Monitor for discussion.

#### **Adverse Events of Special Interest:**

- If an event of iron overload occurs it will be captured as an adverse event of special interest. Iron overload is defined as any liver biopsy findings or MRI imaging consistent with this diagnosis in the setting of persistent TSAT >45%. In the event of an adverse event of special interest, the Investigator must review other prescribed iron supplementation (IV and oral) and make adjustments in accordance with Section 7.1.2.1.
- If a clinically significant episode of hypophosphatemia occurs it will be captured as adverse events of special interest. Clinically significant hypophosphatemia is defined as serum phosphorus <2.5 mg/dL. In the event of an adverse event of special interest, the Investigator must review other prescribed phosphate-lowering therapies and make adjustments in accordance with Section 7.1.2.1.

Subjects will be followed for protocol required SAEs and AEs of special interest until the final required protocol visit or until all drug-related toxicities and AEs have resolved (or are considered chronic/stable), whichever is later.

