#### **9.6.4    Reporting Adverse Events**

Non-serious AEs (with the exception of Adverse Events of Special Interest in Section 9.5.2) will not be collected in source documents or reported in the eCRF.

All SAEs will be collected in source documents and reported in the eCRF.

All Adverse Events of Special Interest will be collected in the source documents and reported in the eCRF.

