### 3.6. Safety Analyses

Hypotheses are not provided for safety outcomes. Observed measures of the following biochemical results will be reported at each visit and change from baseline at each visit: serum phosphorus, ferritin, TSAT, hemoglobin, and eGFR. Additionally, for hemoglobin and serum phosphorus, the proportion of patients within clinical standard of care range, using last on treatment value will be reported.

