#### **Adverse Events of Special Interest:**

- Iron overload is defined as any liver biopsy findings or MRI imaging consistent with this diagnosis in the setting of persistent TSAT >45%.
- Clinically significant hypophosphatemia, defined as serum phosphorus <2.5 mg/dL.

No statistical inference testing will be done for adverse events.

AE analyses, by subject incidence and event counts, will be summarized by preferred terms, within system organ class, by number and percentage for all subjects in the safety population.

All SAEs will be coded using Medical Dictionary for Regulatory Activities (MedDRA). All verbatim terms will be reconciled to preferred terms by the Medical Monitor. Treatment-emergent SAEs will be summarized by system organ class and preferred term (PT) for each treatment group. SAEs will also be summarized by their maximum severity.

A summary and listing of all deaths and cause of death will be provided overall and by treatment group.

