**Table X: Primary Outcome Measures**

**Table X: Secondary Outcome Measures**

**Table X: All Adverse Events**

Type of AE	Ferric Citrate (n, % with event)	Placebo (n, % with event)
Serious AEs		
Related Serious AEs		
Adverse Events of Special Interest (AESI)		

Abbreviations: AE, adverse event.

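### The hypophosphatemia AESI is defined by a laboratory cut-off but collected through site reports, and no planned output counts subjects who ever fell below 2.5 mg/dL

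*Protocol*

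**What the plan says.** **Definition.** Protocol 9.5.2 states "Clinically significant hypophosphatemia is defined as serum phosphorus <2.5 mg/dL", with no requirement for symptoms or a confirmatory value. SAP 3.6.1 repeats the cut-off: "Clinically significant hypophosphatemia, defined as serum phosphorus <2.5 mg/dL". Protocol 7.5.1 likewise equates the AESI with a value below 2.5 mg/dL.

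**Collection.** Protocol 9.5.2 says "If a clinically significant episode of hypophosphatemia occurs it will be captured as adverse events of special interest", and section 9.6.4 adds "All Adverse Events of Special Interest will be collected in the source documents and reported in the eCRF". Section 9.6.4 also says that non-serious adverse events other than AESIs are not collected.

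**Review of results.** Under Phosphorus and Iron Indices, Protocol 9.4 says "the Investigator must independently review these results to assess clinical significance and determine whether study drug dose changes or temporary discontinuation are required". The same section has routine laboratory values from the Schedule of Activities entered in the eCRF.

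**Analysis.** SAP 3.6 says "Observed measures of the following biochemical results will be reported at each visit and change from baseline at each visit: serum phosphorus", followed by ferritin, TSAT, hemoglobin and eGFR. For phosphorus it adds the proportion of patients within a standard-of-care range at the last on-treatment value. The SAP does not give the limits of that range. SAP 3 and 3.4.1 specify quartiles, minimum and maximum for continuous variables, and SAP 3 also plans by-subject listings. In SAP 5, the shell for all adverse events has one row labelled "Adverse Events of Special Interest (AESI)".

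**The concern.** A laboratory-defined event can be counted in full from the laboratory data held. Counting it from site reports adds a step at which events can be lost. The wording makes some loss plausible, because clinical significance is a fixed cut-off in Protocol 9.5.2 and a matter for the Investigator's assessment in 9.4. A site could record a value of 2.4 mg/dL, handle it as a study drug matter, and file no AESI.

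This is an expected risk. Protocol 3.2.2 describes the drug's action as precipitating phosphate in the intestine, and inclusion criterion 4 admits subjects at 3.0 mg/dL, which is 0.5 mg/dL above the AESI cut-off. Protocol 11.9 describes safety oversight only in terms of SAE collection, so the final AESI summary carries much of the evidence on non-serious hypophosphatemia.

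**Working it through.** The documents give no expected AESI rate and no reporting completeness, so there is no figure to reproduce. The check is mainly textual.

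1. *Is the event fully determined by a laboratory value?* Yes (Protocol 9.5.2 and 7.5.1, SAP 3.6.1).
2. *Is that value in the database?* Yes for the scheduled assessments (Protocol 9.4), with phosphorus required at least every 90 days (Protocol Table 2). Only Schedule of Activities values are expressly sent to the eCRF, so an unscheduled low value might exist only as a site report.
3. *Does either document derive the event from those values?* No. SAP 3.6.1 gives the definition but no derivation rule.
4. *Would another planned output count the subjects affected?* No.
   - By-visit statistics describe each visit separately. A minimum below 2.5 mg/dL shows that at least one summarized value was low, but not how many subjects were ever low.
   - By-subject listings identify individuals but are not a count by arm.
   - The in-range proportion uses only the last on-treatment value. Protocol 7.1.2.1 has study drug held below 3.0 mg/dL and allows it to resume on recovery, so a low value can be followed by a normal last value.
5. *Would a missed report reappear in the adverse event data?* Not if the event was non-serious (Protocol 9.6.4).
6. *Does hypophosphatemia have its own row?* Not in any shell. The all-events shell has one AESI row, and the system-organ-class shell has columns only for serious and related serious events. SAP 3.6.1 plans summaries by preferred term, but states MedDRA coding only for SAEs.

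**Illustration with assumed inputs.** Take 200 subjects per arm (Protocol 10.1), true incidences p1 (ferric citrate) and p0 (placebo), and the same capture fraction s in both arms. The incidences and s are assumptions.

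- Reported cases = 200 × p × s. For p1 = 10%, s = 80%: 200 × 0.10 × 0.80 = 16.
- Reported risk difference = s × (p1 − p0). For 10% v 3%, s = 80%: 0.80 × 7.0 = 5.6 points.
- Reported risk ratio = (s × p1)/(s × p0) = p1/p0, so s cancels.

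| Assumed true incidence | s = 100% | s = 80% | s = 60% | s = 40% | Risk ratio |
|---|---|---|---|---|---|
| 5% v 1% | 10 v 2 (4.0) | 8 v 1.6 (3.2) | 6 v 1.2 (2.4) | 4 v 0.8 (1.6) | 5.0 |
| 10% v 3% | 20 v 6 (7.0) | 16 v 4.8 (5.6) | 12 v 3.6 (4.2) | 8 v 2.4 (2.8) | 3.3 |
| 20% v 5% | 40 v 10 (15.0) | 32 v 8 (12.0) | 24 v 6 (9.0) | 16 v 4 (6.0) | 4.0 |

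Cells show expected reported cases, ferric citrate v placebo, with the risk difference in percentage points in brackets.

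**The case against.** The strongest reply is that the protocol, followed as written, loses nothing. Every value below 2.5 mg/dL is an AESI and every AESI must be reported. The assessment in Protocol 9.4 serves "to assess clinical significance and determine whether study drug dose changes or temporary discontinuation are required"; it does not govern AESI reporting. **This stands.** A reader might infer that events are counted only after an Investigator has judged them important, but no such filter is stated. The shared term makes non-reporting possible; withholding a low value would still be a departure from the protocol.

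A reader might also infer that merging the two AESIs in one row causes under-counting. It does not: it only obscures which event occurred. The shells are headed as a selection, SAP 3.6.1 lists the two AESIs separately, and its preferred-term summaries could separate them.

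Nor is it right that low values would be invisible. Planned minima, quartiles and listings would show some. There are other traces too: dose adjustments go in the eCRF (Protocol 7.1.2.1), failure to act on low phosphorus or to monitor it is an important deviation (SAP 3.4.3), and monitors check the eCRF against source (Protocol 11.10.1).

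Finally, SAP 3.6.1 gives a numerical definition that a programmer could apply to the laboratory data, and nothing in it forbids that. This is fair, but the SAP does not say it will be done, and the only collection route described is the site report. None of these safeguards gives a count by arm of subjects ever below the cut-off.

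**Conclusion.** The point holds as a gap in the safety analysis, and it is minor. A purely laboratory-defined AESI is collected by site report, has no stated derivation from recorded values, and has no planned count of subjects ever below 2.5 mg/dL. Under-counting is possible; the documents do not show that it would occur, and its size cannot be estimated from them. The tabulated figures rest on assumed incidences and on equal capture in both arms. Under equal capture, only the absolute counts and the risk difference shrink. No efficacy result is affected, and SAP 3.6.1 plans no inferential testing of adverse events. A laboratory-derived count is complete only for recorded values, so low phosphorus between measurements would be missed by either method.

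**What to change.** In SAP 3.6.1, define the hypophosphatemia AESI for analysis as any recorded phosphorus value below 2.5 mg/dL after the first dose of study drug, from a local or central laboratory, combined with any site-reported event. Use the AESI collection period in Protocol 9.6.5, which runs through the 30-day follow-up visit. Site reports must stay in the definition because some low values may not be in the eCRF laboratory data. List every low value with no matching report. In the SAP 5 shell, replace the single AESI row with separate rows for hypophosphatemia and iron overload, giving subjects and events by arm.

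The cost is SAP wording, one derivation and one extra table row. No new data are needed, and no site procedure or dosing rule changes. The downside is that the reported AESI count may rise.

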## **9.6 Adverse Events and Serious Adverse Events**

### **9.6.1 Definitions of Adverse Events and Serious Adverse Events**

#### **9.6.1.1 Adverse Events**

As defined by the Code of Federal Regulations section 312.32 an adverse event (AE) is any untoward medical occurrence associated with the use of a drug in humans, whether or not considered drug related.

An AE may include medical conditions, signs, and symptoms not previously observed in the subject that emerge during the protocol-specified AE reporting period, including signs or symptoms associated with pre-existing underlying conditions that were not present prior to the AE reporting period.

AEs therefore may include the following:

- All AEs, whether suspected to be causally related to study drug or otherwise
- All AEs secondary to any medication overdose, medication error, abuse, withdrawal, sensitivity, or toxicity
- Illnesses apparently unrelated to study drug, including the worsening of a pre-existing illness
- Injury or accidents.
- Abnormalities in physiological testing or physical examination findings that require clinical intervention or further investigation (beyond ordering a repeat [confirmatory] test)
- Laboratory abnormalities that require clinical intervention or further investigation (beyond ordering a repeat [confirmatory] test) unless they are associated with an already reported clinical event.

